9.1.2 Primary Outcome Measurement Time Points

Duration of the follow up will extend to 6 months post final scan for all aGVHD subjects by chart review.

9.1.3 Response Review

The SUVmax values will be analyzed by Nuclear Medicine and Radiology physicians blinded to the diagnosis and results of the other scan, in a randomized order to avoid bias. IHC values will be assessed by trained Pathologists.

9.2 Secondary Outcome

Healthy subjects group: Biodistribution information and kinetic behavior of the radiotracer.

The secondary outcome is the IHC confirmation of abnormal T cell status in those patients who have had a biopsy.

10 STATISTICAL CONSIDERATIONS

10.1 Statistical Design

Multi-arm prospective study of imaging of aGVHD (one group of highly suspected aGVHD and one group at high risk of developing aGVHD) and healthy volunteers.

10.2 Randomization

No randomization will be done.

10.3 Interim analyses

No interim analyses are planned.

10.4 Descriptive Statistics and Exploratory Data Analysis

(see below)

10.5 Analysis

10.5.1 Analysis Population

Analysis population: all ROIs drawn on various organs, as well as areas with elevated SUV relative to healthy volunteers.

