Day 3 aGVHD mice lacked noticeable symptoms and are at a time point when T cell activation is being initiated, whereas day 10 mice display clinical symptoms and are considered at the peak of T cell activation (data not shown). Disease progression is also reflected via significantly higher total donor T cell numbers (higher total body BLI signal) at day 10 (Fig. 8a) versus day 3 (Fig. 7a) ($p<0.01$; quantitative data not shown). As previously shown [28, 41, 42], *in vivo* (Fig. 7a) and *ex vivo* BLI revealed that donor T cells in aGVHD mice at day 3 had accumulated preferentially in lymphoid organs such as the spleen, mesenteric lymph nodes (MLN) and cervical lymph nodes (CLN). On a separate cohort of mice receiving GFP+ donor T cells we qualitatively confirmed progressively higher donor T cell accumulation within the spleen and CLN from day 3 to day 10. Importantly, [^{18}F]F-AraG PET/CT images taken 1 hour after tracer ($\sim 200 \text{ } \square\text{Ci}$) administration showed qualitatively higher uptake in the CLN in aGVHD versus control mice (Fig. 7b). Quantitative image analysis corroborated our findings revealing significantly higher (~ 1.4 -fold) [^{18}F]F-AraG uptake in the CLNs of aGVHD mice ($p<0.05$, Fig. 7c). At 1 hour, tracer uptake within abdominal organs such as the liver and kidneys obscured the ability to visualize *in vivo* differences in tracer accumulation within the MLN and spleen (Fig. 7b). However, tracer biodistribution studies assessed at 90 minutes after intravenous tracer injection revealed significantly higher [^{18}F]F-AraG accumulation in both the CLN ($p<0.05$; ~ 2.3 -fold) and the MLN ($p<0.05$; ~ 2.0 -fold, (Fig. 7d)), and a trend towards higher uptake in the spleen ($p=0.12$). No significant differences were noted across all other organs between control and aGVHD mice. Thus, at an early stage of disease development prior to clinical symptoms in this model, [^{18}F]F-AraG accumulated in lymphoid organs (MLN, CLN, and spleen) harboring activated T cells and [^{18}F]F-AraG PET imaging enabled visualization of early T cell accumulation within the CLN.

[figure not shown]

Figure 7: Bioluminescence and $[^{18}\text{F}]\text{F-AraG}$ PET Imaging of Donor T Cell Dynamics During the Initiation of T Cell Activation in a Mouse Model of acute GVHD.

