a) Bioluminescence imaging of control and GVHD mice 3 days after HCT revealed homing of luciferase-positive donor T cells to secondary lymphoid organs such as the spleen, cervical lymph nodes (CLN), and mesenteric lymph nodes (MLN) in GVHD mice. **b)** Representative $[^{18}\text{F}]\text{F-AraG}$ PET/CT images (10 minute static scan; 60-70 minutes post-tracer administration; $\sim 200 \mu\text{Ci}$) at this time point showed visibly higher tracer uptake in the CLN of GVHD mice versus control mice ($n=3$ per group). **c)** Quantitative region of interest PET image analysis of the CLN corroborated our qualitative assessments, demonstrating significantly ($*p < 0.05$) higher tracer uptake in the CLN of GVHD mice versus control mice (%ID/g; percentage injected dose per gram of tissue). **d)** Biodistribution studies (90 minutes after tracer administration) also supported our imaging findings showing significantly ($*p < 0.05$) higher tracer uptake in CLNs in GVHD versus control mice. Significantly ($*p < 0.05$) higher tracer uptake was also apparent in the T-cells harboring MLN and a trend ($p=0.12$) towards higher uptake was seen in the spleen. Data in all graphs are expressed as mean \pm SD.

At day 10, at the peak of T cell activation, $[^{18}\text{F}]\text{F-AraG}$ PET/CT images showed an even more apparent increase in tracer accumulation in the CLN of aGVHD compared to control mice (Fig. 8b), which was quantitatively confirmed via PET image analysis (Fig. 8c). Tracer biodistribution analysis revealed significantly lower tracer uptake in the spleen at this time point ($p < 0.05$, Fig. 8d), but higher uptake in both the CLN and the MLN ($p < 0.05$ and $p < 0.01$, respectively). Amongst aGVHD mice, we also showed significantly higher BLI and PET signal within the CLNs at day 10 versus day 3 ($p < 0.05$; Fig. 8e), indicating promise for monitoring disease burden via this surrogate imaging biomarker. These findings were recently published in Cancer Research (77(11); 2893–902, 2017).

[figure not shown]

Figure 8: Bioluminescence and $[^{18}\text{F}]$ -AraG PET Imaging of Donor T Cell Dynamics During the Peak of T Cell Activation in a Mouse Model of acute GVHD

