8.2 Data Management Plan

The study will be registered on Oncore, a centralized database used by CCTO to manage clinical trials. All associated approvals and subject information will also be stored on this platform. Any case report forms (CRFs) will be stored in a locked office in the Nuclear Medicine clinic. Records will be kept using OnCore.

Data will be managed using Excel software where the following important parameters will be documented; subject ID (number assigned based on order of scan), the type of subject (healthy/highly suspected GVHD or high risk GVHD group), sex of the subject and their weight, height and age. The date and time of radiotracer injection, the dose injected, time and duration of PET scan will also be noted.

For data analysis the following parameters will be documented; region of interest (e.g. liver, heart, cervical lymph nodes), volume of the region of interest and the associated mean, maximum and minimum values for the Standard Uptake Values (SUV).

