9.1.1 Primary Outcome Measurement Methods

Static images acquired will be used to determine the bio-distribution of the imaging agent in the GVHD groups. Past images as well as newly acquired data from healthy subjects will be used as comparisons. Regions of interest will be drawn on various organs such as the liver, cervical lymph nodes and gut and quantified using imaging software (e.g. Inveon Research Workplace or Amide). In addition any areas that show up differently in the GVHD groups, to the normal bio-distribution seen in healthy subjects will be identified and ROIs will also be drawn over these regions.

Bio-distribution data will be expressed as % injected dose/gram (%ID/g) and/or as standard uptake values (SUV) with respect to the organ being studied. In the high suspected aGVHD group, [¹⁸F]F-AraG PET results will be compared to any grades and scores of aGVHD severity attributed to subjects. In the case of the high-risk group, after the second scan, patients will be monitored for development of aGVHD and the clinical endpoint (whether or not the high risk patient develop aGVHD) will represent the primary outcome variable. In addition, IHC analysis of biopsies taken in either GVHD group will help in the interpretation of the primary results and thus potentially support interpretation of the PET data. The IHC analysis will involve determining the amount of cell death or T cell infiltration and activation.

Vital signs and blood laboratory data collected before and after the i.v. injection of [¹⁸F]F-AraG will allow evaluation of any unexpected side effects.

To measure plasma radioactivity, whole blood sample will be centrifuged. The radiolabeled tracer concentration in whole blood, pellet post centrifugation and plasma will be measured by a gamma well counter (1-min per sample). The counting rates measured by the well counter will be converted to the PET equivalent counts using a conversion factor from a weekly phantom cylinder study. The counts should be decay corrected back to the injection time.

Plasma parent tracer and metabolite concentrations will be determined using solid phase extraction combined with HPLC technology.

Clinical assessment of disease severity will be made by the aGVHD grade. Staging and grading of the disease will be performed by Clinicians at the Bone Marrow and Transplant Clinic using the Glucksberg grade and International bone marrow Transplant Registry Severity Index (IBMTR) at time of enrollment and imaging.

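### Extra areas with reduced uptake get an ROI but no place in the analysis set, and the Arm 1 statistic would largely miss a fall in the spleen

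*Combined protocol and SAP*

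**What the plan says.** Section 9.1.1 describes two kinds of ROI. The first is anatomical: "Regions of interest will be drawn on various organs such as the liver, cervical lymph nodes and gut and quantified using imaging software". The second is found by comparison: "In addition any areas that show up differently in the GVHD groups, to the normal bio-distribution seen in healthy subjects will be identified". Each area found in this way is then outlined and quantified as well. No direction is attached to the second kind.

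Section 10.5.1 then sets the primary analysis set: "Analysis population: all ROIs drawn on various organs, as well as areas with elevated SUV relative to healthy volunteers".

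Section 8.2 says what is recorded for analysis: "region of interest (e.g. liver, heart, cervical lymph nodes" being its examples, together with ROI volume and mean, maximum and minimum SUV. Both organ lists are open, and neither names the spleen.

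For the highly suspected group (Arm 1), 10.5.2 plans one statistic beyond description: a Spearman correlation of severity with the median or the maximum SUV over ROIs. For the high-risk group (Arm 2) it plans a correlation between the two scans and a logistic regression of later aGVHD on SUV.

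On the spleen, section 2.2 reports for day 10 mice: "Tracer biodistribution analysis revealed significantly lower tracer uptake in the spleen at this time point" (p<0.05), with cervical and mesenteric nodes higher than control. At day 3 it reports "a trend towards higher uptake in the spleen" (p=0.12). It also says that the spleen is known to hold activated donor T cells in this model.

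**The concern.** The section that defines the measurements accepts a difference in either direction, while the section that defines the analysis accepts only a rise for the extra areas. A region that goes cold in disease would be drawn, quantified and then left without an analysis.

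The spleen raises a related question. It is the organ in which the sponsor has already seen uptake fall in symptomatic animals while nodes rose. If no spleen ROI is drawn, the spleen can reach the analysis only as an extra area, and that route is closed to a fall. If one is drawn, its value goes into a median or maximum with organs that may be moving the other way. A first pilot in this disease should learn where the signal appears and in which direction before the larger phase II study foreseen in 10.9.

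**Working it through.** No power, alpha or effect size is stated that could be reproduced. The check compares the sections and then looks at how the Arm 1 summary behaves.

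**Step 1. Which ROIs enter the analysis set**

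| ROI type | Higher than healthy | Lower than healthy |
|---|---|---|
| Organ ROI | drawn (9.1.1), in (10.5.1) | drawn (9.1.1), in (10.5.1) |
| Extra area | drawn (9.1.1), in (10.5.1) | drawn (9.1.1), **not covered** (10.5.1) |

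One cell of four is dropped. A spleen ROI drawn as an organ is in the top row and is kept.

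**Step 2. Is a spleen ROI assured?** No. Section 9.1.1 names liver, cervical nodes and gut; 8.2 names liver, heart and cervical nodes. The spleen can be imaged in people: the legend to Fig. 9 reports uptake there, and Table 2 gives it the third-highest organ dose after kidneys and liver in both sexes (0.0936 rem/mCi in males, 0.1637 in females). Table 1 gives no spleen SUV, so the documents hold no healthy reference value for it.

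**Step 3. What the Arm 1 summary does with a spleen fall**

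Assume for illustration that the ROIs are the three organs named in 8.2 plus the spleen. Take the healthy mean SUVmax from Table 1: heart 4.72, cervical node 7.13, liver 16.18. Call the unknown spleen value s.

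*Maximum.* max(4.72, 7.13, 16.18, s) = 16.18 for every s up to 16.18, so no fall from such a value changes it. A fall registers only if s starts above the liver, and then only down to 16.18. If kidneys were also drawn (SUVmax 44.47 right, 41.35 left), they would set the maximum instead.

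*Median of four values* (the mean of the middle two):
- s below 4.72: (4.72 + 7.13)/2 = 5.925, whatever s is.
- s from 4.72 to 16.18: (s + 7.13)/2, so a fall counts at half its size.
- s above 16.18: (7.13 + 16.18)/2 = 11.655, whatever s is.

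In the middle case, if the spleen falls by x and the node rises by x, the median is ((s − x) + (7.13 + x))/2 = (s + 7.13)/2. It does not move as long as these two remain the middle values. That is the pattern of signs seen in the day 10 mice.

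The exact figures depend on the assumed ROI set and on healthy group means. What carries over is that the maximum ignores a fall in any organ that does not hold it, and the median dilutes or cancels one.

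**Step 4. Strength of the mouse evidence.** The day 10 fall comes from ex vivo tissue counting, not imaging. The Fig. 8 legend gives 4 aGVHD and 3 control animals under its PET panel and no separate count for the tissue data. The day 3 trend was not significant.

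**The case against.** The strongest reply is that the mismatch is small. The word elevated qualifies only the extra areas. The organ ROIs come first in the same sentence without condition, the spleen is an organ, and the lists are open, so not naming it does not exclude it. The documents give no example of a reduced-uptake area outside the organs. This stands, and it confines the gap in 10.5.1 to one cell.

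Second, the animal basis is thin. Section 2.2 concedes that spleen differences could not be seen in vivo in the mice. Arm 1 patients may also have had up to 7 days of steroids, so day 10 mice are an imperfect model for them. This stands too: it makes the spleen worth recording but does not predict what patients will show.

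Third, the pooled summary is specified for Arm 1 only. In Arm 2 a negative logistic coefficient could pick up a fall, and descriptive statistics are planned throughout. This limits the pooling problem to Arm 1. It does not settle whether a spleen ROI exists to be described.

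Fourth, rewording 10.5.1 alone would not change how the spleen is handled, and it would put low-uptake areas into the same pooled median. That is correct, and the fix has to allow for it.

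**Conclusion.** Two modest points hold. Sections 9.1.1 and 10.5.1 disagree on extra areas with reduced uptake, which are measured but not analysed. Separately, the spleen is not assured an ROI, and if it has one, the Arm 1 median or maximum is poorly suited to show a fall in it. The second point rests on liver or another high-uptake organ being among the pooled ROIs; liver is named in both lists.

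A reader might infer that 10.5.1 keeps only elevated areas and so removes the spleen. The text does not support that, because organ ROIs enter whatever their uptake. A reader might also infer that the spleen is the only sign in the animal data that separates early from late disease. It is not: cervical-node PET signal was significantly higher at day 10 than at day 3 (p<0.05), and cervical nodes are a named ROI.

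No sample size, error rate or power claim is affected. The study has up to 25 patients, roughly half per arm, and 10.7 says it lacks power for formal tests. This is a cheap improvement.

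**What to change.** 1. In 9.1.1 and 8.2, name the spleen as a fixed ROI in every patient and healthy-volunteer scan. The 5 planned healthy volunteers would then supply the reference values that Table 1 lacks.
2. In 10.5.2, report spleen SUV separately and two-sided, labelled exploratory: against severity in Arm 1, and by scan in Arm 2.
3. Leave the spleen out of the median or maximum over ROIs.
4. In 10.5.1, include extra areas with reduced as well as elevated SUV, to match 9.1.1, and summarise the two directions separately so that they are not pooled.

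The cost is some wording and one more ROI on scans already planned, with no added scan, radiation or patient. The small downside is a few more exploratory comparisons in a pilot that claims no power, so they should be presented as descriptive.

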10.5.2 Analysis Plan

Although the study will have low power due to the constrained sample size, in addition to descriptive statistics we will perform the following statistical analyses:

- In the highly suspected group:
Spearman rank correlation between median or maximum SUV values across ROIs and disease severity
- In the high-risk group:
Spearman rank correlation between SUV values in the first and second scans prediction of disease status at end of follow-up (aGVHD or no aGVHD) from SUV values of the first and second scans (using logistic regression)

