The suitability of [¹⁸F]F-AraG for human studies has been validated in humans at the University of California San Francisco (UCSF). [¹⁸F]F-AraG PET/CT scans were performed on six healthy human volunteers and dosimetry was also calculated. [¹⁸F]F-AraG exhibited hepatobiliary and renal clearance with highest uptake in associated organs with SUV mean values (normalized to body weight) of 13.47 \pm 1.46, 20.72 \pm 5.26 and 17.27 \pm 4.19 in liver, right and left kidneys respectively at 47-77 minutes post tracer injection (Table 1). High uptake was also observed in the myocardium as seen in mice, while relatively low background was observed in the thorax and lower abdomen. No significant adverse events or blood lab changes were observed due to

tracer administration in any of the volunteers other than slightly increased urine esterase levels. Radiation dosimetry results are shown in Table 2. These findings were recently published in Cancer Research (77(11); 2893–902, 2017).

[figure not shown]

Fig. 9: Whole body PET images of $[^{18}\text{F}]\text{F-AraG}$ in a healthy human volunteer. Frontal (top panel) and dorsal (bottom panel) coronal PET images taken immediately after intra-venous injection of the tracer and at serial time points in one of the 6 humans imaged. Highest activity is observed in the liver, kidneys and bladder, associated with $[^{18}\text{F}]\text{F-AraG}$ clearance from the body. Uptake is also observed in the heart and spleen while relatively low background activity is observed in all other tissues. Similar images were obtained from the other 5 subjects.

Site	SUV-BW _{mean}	SUV-BW _{max}
Brain Tissue	0.02 ± 0.01	0.08 ± 0.02
Cervical Lymph Node	5.2 ± 1.15	7.13 ± 1.76
Heart	2.12 ± 0.72	4.72 ± 1.37
Myocardium	3.38 ± 1.19	4.72 ± 1.37
Liver	13.47 ± 1.46	16.18 ± 2.00
Kidney (right)	20.72 ± 5.26	44.47 ± 12.44
Kidney (left)	17.27 ± 4.19	41.35 ± 10.65
Bladder	8.28 ± 6.15	10.28 ± 7.66
Muscle	0.98 ± 0.44	1.42 ± 0.66

Table 1: $[^{18}\text{F}]\text{F-AraG}$ standard uptake values for key tissues- normalized to body weight (SUV-BW) at 47-77 minutes post tracer injection in six healthy human volunteers.

SUV-BW mean and max values shown. Data shown represent averages \pm standard deviation; n=6 for each site. Average of both right and left sides of subject shown for brain tissue and cervical lymph node.

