These preliminary studies in healthy human volunteers have been promising with low background in the thorax and GI tract, making it favorable for thoracic and pelvic imaging. Favorable kinetics of [¹⁸F]F-AraG in humans along with the preclinical data support its potential as a promising tracer for early detection of GVHD and warrants its further clinical evaluation in aGVHD patients. Given the paucity of PET tracers for activated T cells in the clinic this work lays the important foundation for [¹⁸F]F-AraG PET imaging in aGVHD patients and the potential to provide crucial information to aid in the detection of activated T cell dynamics during the activation phase of aGVHD.

Organs	Male	Female
Adrenals	0.046567	0.067133
Brain	0.006380	0.007407
Breasts	0.005757	0.007547
Gallbladder Wall	0.051400	0.063033
LLI Wall	0.085107	0.012150
Small Intestine	0.047033	0.073000
Stomach Wall	0.018667	0.025367
ULI Wall	0.022600	0.033067
Heart Wall	0.052533	0.096933
Kidneys	0.877000	1.133333
Liver	0.211000	0.266667
Lungs	0.027167	0.033133
Muscle	0.009190	0.012167
Ovaries		0.016967
Pancreas	0.037300	0.050200
Red Marrow	0.013600	0.016833
Osteogenic Cells	0.007390	0.010593
Skin	0.004543	0.005790
Spleen	0.093600	0.163667
Testes	0.002780	
Thymus	0.005710	0.007800
Thyroid	0.001357	0.001633
Urinary Bladder Wall	0.085800	0.088167
Uterus	0.014133	0.017500
Total Body	0.018767	0.025200
Effective Dose	0.0138 mSv/MBq	

Table 2: [¹⁸F]F-AraG human radiation dosimetry data. Mean radiation dosimetry data in 3 males and 3 females in REM/mCi. The kidneys receive the highest radiation dose followed by the liver.

For our studies at Stanford, the tracer will be administered as a single bolus injection of approximately 5 mCi into a hand or arm vein. The rationale for the starting dose is based on dosimetry studies already performed in healthy human volunteers where the dose limiting organ was found to be the kidney and the annual dose characterized as 5mCi. Please refer to the imaging protocol for recommended limits for male and female subjects. The major route of clearance based on initial clinical studies is the liver and kidney.

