19. After $[^{18}\text{F}]\text{F-AraG}$ injection, participants will be asked to return to the clinic for a safety follow-up visit for blood sample collection for blood chemistry and hematology and also for measurements of vital signs. Results will be recorded in the case report form.

GVHD patient protocol

1. Subject will be asked to drink 1-2 glasses of water before his/her arrival at the clinic.
2. Subject will be consented by a member of the study team
3. Subject will be weighed.
4. The subject will likely have an existing port (double lumen catheters) for administration of the radiotracer.
5. A blood sample will be taken 5-120 minutes prior to the injection of the tracer, to be used for baseline chemistry and hematology laboratory testing. Blood pressure, temperature, heart rate and pulse oximetry measurements will also be taken up between 5-120 minutes prior to injection (baseline).
6. $[^{18}\text{F}]\text{F-AraG}$ formulated in a sterile and pyrogen-free isotonic solution will be administered in a single slow IV injection. The line will be flushed with at least 10 ml normal saline after injection. The bed strap should be open until scanning starts.
7. A small low activity calibration source of known activity of F-18 will be placed in the field of view in each image collected
8. Participants will have a static PET scan at 60 minutes after injection of $[^{18}\text{F}]\text{F-AraG}$ covering all positions from vertex to toe. Attenuation correction will be done with a CT scan (120 kv, 10 mA) usually acquired before the PET scan. There will be 8 bed positions covering head to toe (each position will take approximately 3 minutes). The data should be collected in list mode and saved. Patients that are able to tolerate longer times in the scanner will also undergo an additional scans following the same format described above at 30 minutes post tracer injection.
9. All recordings of important time measurements (e.g. time of injection and acquisitions) will be done using the same clock e.g. a phone.
10. Blood pressure, temperature, respiratory rate, heart rate and pulse oximetry measurements will be taken immediately after the $[^{18}\text{F}]\text{F-AraG}$ PET-CT scan.
11. Participants will be asked to void as frequently as possible to reduce radiation exposure.
12. Participants will be given a copy of the consent form they signed and will be dismissed.

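### The Arm 1 severity correlation may be taken on a raw maximum SUV that clearance organs are likely to set, or on a median that depends on an open ROI list

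*Combined protocol and SAP*

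**What the plan says.** Section 9.1 makes the severity of aGVHD the primary outcome in the highly suspected group (Arm 1). The one planned correlation with severity is in section 10.5.2: "Spearman rank correlation between median or maximum SUV values across ROIs and disease severity". Section 10.5.1 defines the input: "Analysis population: all ROIs drawn on various organs, as well as areas with elevated SUV relative to healthy volunteers". Neither section chooses between median and maximum, excludes an organ, or scales SUV to a reference.

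The ROI list is open. Section 9.1.1 says "Regions of interest will be drawn on various organs such as the liver, cervical lymph nodes and gut", and then "In addition any areas that show up differently in the GVHD groups, to the normal bio-distribution seen in healthy subjects will be identified". Section 8.2 gives another example list, with liver, heart and cervical nodes but no gut. Liver is in both lists. Kidney is in neither, but nothing excludes it. Section 9.1.3 indicates that SUVmax is the value read.

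On normal uptake, section 2.2 reports that the tracer "exhibited hepatobiliary and renal clearance with highest uptake in associated organs", and describes "low background in the thorax and GI tract, making it favorable for thoracic and pelvic imaging". Table 1 gives the values for six healthy volunteers at 47 to 77 minutes. The patient scan falls inside that window (section 5.1): "Participants will have a static PET scan at 60 minutes after injection".

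**The concern.** A maximum over pooled organs reports whichever organ has the highest uptake. Where normal liver uptake is well above that of nodes, and gut background is low, a moderate rise in gut or nodes leaves the maximum unchanged. The correlation then mainly ranks patients by clearance-organ uptake. A rho near zero could be read as no link between tracer and severity although gut or nodal uptake does track it. More patients would not cure this, because the fault lies in the summary measure.

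The median has a different weakness. It depends on how many low-uptake and high-uptake organs the reader draws, and the set can differ between patients because areas that look abnormal are added.

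**Working it through.** The plan gives no target correlation, alpha or power for this analysis, so there is no figure to reproduce.

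**Step 1. Inputs (Table 1, SUVmax, mean ± SD, n = 6).** Liver 16.18 ± 2.00; cervical node 7.13 ± 1.76; heart 4.72 ± 1.37; muscle 1.42 ± 0.66; right kidney 44.47 ± 12.44; left kidney 41.35 ± 10.65.

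**Step 2. Probability that liver exceeds a lesion of SUVmax m.** Normal: Φ((16.18 − m)/2.00). For m = 12 this is Φ(4.18/2.00) = Φ(2.09) = 98%. To allow for only six volunteers, use t with 5 df and SD 2.00 × √(7/6).

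| m | 10 | 12 | 14 | 16 | 18 | 20 |
|---|---|---|---|---|---|---|
| normal | 99.9% | 98% | 86% | 54% | 18% | 3% |
| t, 5 df | 98% | 94% | 82% | 53% | 22% | 7% |

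The crossover is close to 16. If lesion uptake itself varies (SD 1 to 4), liver still wins in 83 to 97% at a lesion mean of 12 and in 52 to 53% at 16.

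**Step 3. Kidneys.** If they are drawn, at least one exceeds liver with probability above 99.9% (normal, treated as independent). The maximum is then renal.

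**Step 4. Nodes.** A node must rise 16.18/7.13 = 2.27-fold to equal mean liver. Section 2.2 gives day 3 mouse ratios of about 1.4 (cervical node, PET), 2.0 (mesenteric node, tissue counts) and 2.3 (cervical node, tissue counts). If these transfer to human SUVmax (an assumption), node means are 7.13 × 1.4 = 10.0, 7.13 × 2.0 = 14.3 and 7.13 × 2.3 = 16.4. With the node SD scaled by the same ratio f, P(liver > node) = Φ((16.18 − 7.13f)/√(2.00² + (1.76f)²)) = 97%, 68% and 48%; the t version gives 93%, 65% and 48%.

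**Step 5. Effect on rho (illustration only).** Assumptions: 12 patients, grades 1 to 4 equally likely, 10,000 simulated trials. Gut SUVmax = 2 + slope × grade with SD 1.5, skin 1.0 with SD 0.4, and other organs as in Table 1, unrelated to grade. No kidney is drawn. Mean Spearman rho with grade:

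| Gut slope | 1.5 | 2 | 2.5 | 4 |
|---|---|---|---|---|
| raw maximum | 0.00 | 0.00 | 0.00 | 0.36 |
| gut alone | 0.72 | 0.81 | 0.86 | 0.93 |
| median of liver, node, gut | 0.30 | 0.56 | 0.74 | 0.88 |
| maximum of gut, node, skin | 0.30 | 0.56 | 0.74 | 0.91 |

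Adding heart and muscle moves the median from 0.88 to 0.30 at slope 4, and from 0.30 to 0.50 at slope 1.5. The ROI list can therefore shift it in either direction.

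If only liver carries the signal (1 or 2 SUV per grade), the raw maximum gives 0.47 or 0.72, liver alone gives the same, and the non-liver maximum gives 0.

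**The case against.** **The plan also allows the median.** Over the three organs named in section 9.1.1 it does about as well in the gut runs as a maximum that leaves liver out. This stands. A reader might infer that the plan cannot detect a gut signal; that is too strong, because only one of the two permitted summaries fails in this way. What remains is that neither the summary nor the list is fixed.

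**Removing liver is not a clean remedy.** This also stands. Nodes set the non-liver maximum in 68% of simulated patients at gut slope 1.5 and in 52% at slope 2, so it masks a modest gut signal. It also discards any liver signal, although liver is a staging organ in section 9.1.

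**The mouse ratios are from day 3, before symptoms.** Arm 1 patients are highly suspected and need systemic therapy. Section 2.2 reports a clearer nodal increase at day 10 but gives no ratio. The day 3 figures may therefore understate Arm 1 uptake.

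**The harm is bounded.** The correlation comes in addition to descriptive statistics. Section 8.2 stores mean, maximum and minimum SUV for each ROI. Section 10.6.2 plans a site-level correlation of SUV with IHC. Section 10.7 disclaims power for formal tests. With 12 patients an approximate 95% interval around rho = 0 is tanh(±1.96 × √(1.06/9)) = ±0.59, so a value near zero could not establish the absence of an association. All this limits the consequence. It does not make the pooled maximum interpretable, and the IHC correlation does not address severity.

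**Conclusion.** The point holds in limited form. As written, sections 10.5.1 and 10.5.2 permit a raw maximum that liver would set in most patients until lesion SUVmax nears 16, if liver is drawn and kidneys are not, and that the kidneys would set if they are drawn. It can hide a gut or nodal association. It stays informative only if liver, not kidney, sets it and liver uptake itself tracks severity, or if lesions exceed the highest clearance organ drawn. The permitted median largely avoids this for liver, cervical nodes and gut but is not defined until the ROI list is closed.

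The probabilities assume that Table 1 uptake in six healthy volunteers carries over to transplant patients. The rho values show direction only, since the documents give no SUV from an aGVHD patient. A reader might infer that the Arm 1 result will be null or that the trial will miss the disease. The documents do not support that: they do not say which organ carries the signal, and they do not commit to the maximum. No decision rule uses this rho; the move to Arm 2 (section 10.8) rests on whether the tracer can image the disease. Severity: minor to should-fix.

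**What to change.** In sections 10.5.1 and 10.5.2:

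1. Name one set of target-organ ROIs to be drawn in every Arm 1 patient, for example gut, liver, skin and cervical nodes, and exclude kidney and bladder.
2. Drop the pooled raw maximum. Report Spearman's rho with severity separately for each organ, liver included, each with an interval.
3. Name in advance the main correlation: either one organ-level correlation or one pooled summary over the fixed list. Treat the others as descriptive. The non-liver maximum should not be the default, for the reasons given above.
4. Report areas added because they looked abnormal separately, in line with the per-lesion assessment in section 1.1.

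The cost is SAP wording, a few more correlations and slightly more ROI drawing, with no new scans. Because more correlations will be shown, step 3 is needed so that the largest is not picked afterwards.
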